**Table 1. Visit Assignments for Clinical Rating Scales Assessments**

Derived Visit	Target Study Day*	Time Interval (Study Day Range)
Baseline (Day 1)	1	Last value on or before the first dose
Week 2	15	2 – 21
Week 4	29	22 – 42
Week 12	85	43 – 126
Week 24	169	127 – 210
Week 36	253	211 – 294
Week 48	337	295 – 421
Week 72	505	422 – 589
Week 96	673	590 – 757
Week 120	841	758 – 925
Week 144	1009	926 – 1093
Week 168	1177	1094 – 1261
Week 192	1345	1262 – 1429
>Week 192	1513	1430 and up

\*Target study day is relative to date of first dose in the ACP-103-015 study.

The study day is defined as:

For visits on or after the reference day: study day = visit day – reference day +1

For visits before the reference day: study day = visit day – reference day where the reference day equals the start day of study drug in the ACP-103-015 study.

#### 5.4.2 Summary Time Periods for Safety Results

For safety assessments (AEs, laboratory tests, vital signs, ECG data, UPDRS II+III and physical examinations), the data summary will be based on chronological time periods as defined in [Table 2](#). Rules for determining the analysis values within each time period are detailed in [Section 5.13](#).

**Table 2. Safety Summary Time Periods**

Time Period	Study Day Range	
	AE Onset	Other Safety Measurement
Baseline	N / A	Last value on or before the first dose
First 4 weeks	1* - 28	2* - 28
1 – 3 months	29 – 91	29 – 91
>3 – 6 months	92 – 183	92 – 183
>6 – 12 months	184 – 365	184 – 365
>1 – 2 years	366 – 730	366 – 730
>2 – 3 years	731 – 1095	731 – 1095
>3 – 4 years	1096 – 1461	1096 – 1461
>4 years	>= 1462	>= 1462

\* Protocol procedures specified that all baseline assessments were to be done before administration of study drug on Day 1. For conservative reason, AEs started on Day 1 are considered “post-baseline”.

### 5.4.3 Missing Values

Unless otherwise specified, missing values will not be imputed for any of the rating scales or questionnaires. A missing value is defined as one which is blank, not done, or not applicable on the eCRF. If a scale has a “Not Assessed” response, then that value will be considered a missing value for analysis. In addition, if one or more items in a given subscale is missing then the entire subscale will be set to missing. In case a questionnaire consists of more than 1 subscale, any non-missing subscales will be used for analysis. For example, if in the SAPS scale the Hallucination subscale has a missing item, but the Delusion subscale is complete, then the Delusion subscale will be analyzed per the analysis plan. For the CGI-S and CGI-I questionnaires, a response of “Not assessed” will be treated as a missing value as well.

For questionnaires that utilize a total score (NMSS, Caregiver Burden Scale), if any of the individual items that contribute to the total score are missing, the total score will also be set to missing.

Missing baseline assessments will not be imputed. However, the SAPS and CGI-S scales were not collected at the ACP-103-015 baseline; therefore, the last core study assessment will serve as the ACP-103-015 baseline assessment for these scales.

Missing dates for AEs and concomitant medications will be imputed for the purpose of establishing the time of event in relation to study treatment. All data listings will display data as reported on the eCRF. When AE onset date or concomitant medication dates are missing or incomplete, the study days (onset or start day relative to first dose date) will be calculated based on imputed value.

The imputation rules for AE/concomitant medication start dates are as follows:

- If a full date is missing, impute date as date of first dose (study day 1);

- If the day component is missing from full date, date is imputed as study day 1 if the date is in the same month and year as first dose, otherwise impute as the 1st of the month;
- If the month and day components are missing from full date, but year is present, the date is imputed as January 1 if the year is different than the year of first dose, or imputed as the first dose date if the year is the same as the year of first dose;
- If any of the above imputations result in a start date which is later than an existing complete end date, the start date will be set equal to the end date.

Missing end dates for AE will not be imputed.

The imputation rules for concomitant medication end date are as follows:

- If a full date is missing and the status of the medication is not ongoing, impute date as the last dose date;
- If the day component is missing from full date, impute date as the last day of the month;
- If the month and day components are missing from full date, but year is present, the date is imputed as last dose date if the year is the same as the last dose date and medication start date is prior to last dose date, otherwise impute as the last day of the year;
- If any of the above imputations result in the medication end date which is prior to the medication start date, the medication end date will be set equal to the medication start date.

For AE listing, AEs missing severity or relationship will be displayed as missing to reflect the raw data collected on eCRF. For AE summary by severity, AEs with a missing severity will be tabulated as “severe”. AEs with missing relationship will be tabulated as related.

The last dose date is collected on the discharge eCRF. If a subject has withdrawn from the study, but the last dose date is reported as a partial date, then the last dose date will be imputed using logical algorithms utilizing other reported data (e.g. death date if died, AE end date if discontinued due to AE, maximum projected dose date based on last dispensed and returned tablets, database snapshot date, ...etc). The complete programming algorithms are detailed in a separate programming specification document.

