### **5.9.2 Prior, Post and Concomitant Medications**

Medications started prior to the day of the first dose of open-label study medication and continued into the study, or medications started on or after the day of the first dose of study medication and before or on the day of the last dose of the study medication will be reported as concomitant medications. Medications stopped before the first date of study medication dosing will be considered prior medications. Medications started after

the day of last dose of study medication will be considered post-treatment. Prior, concomitant and post-treatment medications will be listed.

The number and percentage of subjects using concomitant medications in each WHO Drug Anatomical/Therapeutic/Chemical (ATC) Level 3 (i.e., pharmacological subgroup) category and preferred term will be summarized. Separate summaries will be presented for

- Anti-psychotic medications
- Medications indicated for dementia
- Medications indicated for motor function
- Medications not included in the preceding 3 categories.

Number of concomitant medications will be summarized at first dose date and last dose date for overall, indicated for motor functions, dementia and antipsychotics.

Antipsychotics taken post-treatment (medication started after the last dose date) will also be summarized. Multiple medications for the same subject may be classified to the same ATC level or preferred name. However, subjects will only be counted once for each level of classification.

Prior, concomitant, and post-treatment medications with the verbatim, ATC level 3 category, preferred term, indication, dosage, route, unit, frequency, and start/stop dates of administration will be provided in a listing.

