- (1) AEs grouped by time period at AE onset: For all TEAEs, serious TEAEs, TEAEs leading to discontinuation of study drug, and TEAEs of special interest (those that may be expected on the basis of pimavanserin's pharmacology, those of special regulatory interest [suicidality, abuse liability etc], and those commonly associated with current antipsychotics), the count and percentage of subjects will be summarized by time period defined in [Section 5.4.2 Table 2](#). The denominator for a time period will be the number of subjects on treatment

(including a 30-day follow-up) during that particular time period. TEAEs with fatal outcome will be summarized by time period at death.

- (2) AEs by age group at AE onset: For all TEAEs, serious TEAEs, TEAEs leading to discontinuation of treatment, and TEAEs of special interest, the count and percentage of subjects will be summarized by age category at the time of AE onset. Age at onset will be categorized as follows:  $\leq 50$  years, 51 - 60 years, 61 – 70 years, 71 – 80 years and 81 - 90 years. The denominator for an age group will be the number of subjects on treatment (including a 30-day follow-up) while in that particular age group. TEAEs with fatal outcome will be summarized by age group at death.

An AE listing by subject will display all events and will include the verbatim term in addition to the MedDRA SOC and preferred term. This listing will also include all relevant CRF data associated with the event: date of onset, date of last dose, severity, outcome, relationship to study drug, action taken, and seriousness.

In addition, AE tables also will be summarized by age group and onset time period for subject with concomitant antipsychotic use and without antipsychotic use.

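### When a medication's start is unknown (or year-only in the first-dose year) and its stop is partial but wholly before first dose, SAP 5.4.3 turns a prior drug into a concomitant one

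*SAP*

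**What the plan says.** SAP 5.4.3 imputes medication start dates as follows.

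- No start date at all: "If a full date is missing, impute date as date of first dose (study day 1".
- Year only: 1 January of that year if it is not the first-dose year, "or imputed as the first dose date if the year is the same as the year of first dose".
- A guard follows. If imputation gives "a start date which is later than an existing complete end date, the start date will be set equal to the end date". It refers only to an end date that is complete.

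For medication end dates, a missing day becomes the last day of the month. A year-only date becomes the last dose date or 31 December, depending on the year. If the imputed end date is "prior to the medication start date, the medication end date will be set equal to the medication start date".

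SAP 5.9.2 then classifies by date: "Medications stopped before the first date of study medication dosing will be considered prior medications". A drug started from the first to the last dosing day is concomitant. Two outputs rest on that class:

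- "Number of concomitant medications will be summarized at first dose date and last dose date", with antipsychotics as one of the groups;
- in SAP 5.13.1, "AE tables also will be summarized by age group and onset time period for subject with concomitant antipsychotic use and without antipsychotic use".

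**The concern.** The start-date guard and the end-date rule do not fit together. The guard protects a drug that ended before the study only if its stop date is complete. When only the month or year of stopping is known, the guard is silent, and the end-date rule settles the conflict the other way: it keeps the invented start and discards the recorded stop. SAP 0 (Revision History) says the medication end-date rules were added in this amendment, which may be how the gap arose.

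Antipsychotics are the class where this matters most. Protocol 1 describes off-label use of clozapine and quetiapine in this disease, so stopped antipsychotics in the medication records are plausible. One such record with the affected date pattern would count as an antipsychotic at first dose. It would also move a subject with no on-study use from one side of the AE split to the other, which changes both groups.

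**Working it through.** The plan gives no figure to reproduce. The check applies the written rules to defined date patterns.

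**Inputs.** The start and end rules of SAP 5.4.3 and the classes of SAP 5.9.2. Assumed for illustration: first dose 15 June 2010, last dose 20 September 2011, start dates imputed before end dates.

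**Worked example.** Start missing, stop recorded as March 2010.

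1. Start is imputed as 15 June 2010.
2. The start guard does not apply, because the stop is not complete.
3. Stop is imputed as 31 March 2010.
4. 31 March precedes 15 June, so the stop is moved to 15 June 2010.
5. The record runs from 15 June to 15 June: concomitant.

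With a complete stop of 20 March 2010, the guard applies at step 2. Start and stop are both 20 March, and the drug is prior.

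**All patterns.** Every start/stop pair with start on or before stop was taken on a 5-day grid from 1 January 2008 up to first dose. The 896 days give 180 grid dates. Each start was recorded as complete, month/year, year only or missing, and each stop as complete, month/year or year only. Only records whose stop, at its latest possible date, precedes first dose were kept:

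- complete stop: 180 × 181 / 2 = 16,290 pairs;
- month/year stop (before June 2010; 177 dates): 177 × 178 / 2 = 15,753;
- year-only stop (before 2010; 147 dates): 147 × 148 / 2 = 10,878.

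Records classed as concomitant although the stop field shows they ended before first dose:

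| Start recorded as | Stop complete | Stop month/year | Stop year only |
|---|---|---|---|
| Complete | 0 / 16,290 | 0 / 15,753 | 0 / 10,878 |
| Month/year | 0 / 16,290 | 0 / 15,753 | 0 / 10,878 |
| Year only | 0 / 16,290 | 465 / 15,753 | 0 / 10,878 |
| Missing | 0 / 16,290 | 15,753 / 15,753 | 10,878 / 10,878 |

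The 465 are the pairs with both dates in January to May 2010: 177 − 147 = 30 grid dates, and 30 × 31 / 2 = 465, or 3% of 15,753. Their year-only start falls in the first-dose year. Year-only start with year-only stop gives none, because a stop year that ends before first dose cannot be the first-dose year.

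These are counts of date combinations, not expected numbers of patients.

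**With the check proposed below.** The start is capped at the latest date that the partial stop allows, when that date precedes first dose. The misclassified count falls to 0 in all 12 patterns. The worked example becomes 31 March to 31 March 2010: prior.

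**The case against.** The strongest reply is that the gap is narrow and the outputs are secondary. Both dates must be defective, and 9 of the 12 patterns are handled correctly. The study is descriptive. TEAE, SAE and mortality totals do not depend on medication dates. Listings show dates as reported, so a reader can find the affected records. Protocol 3.6.2.1 requires the baseline medication review only for subjects who enter more than one week after the core study, and Protocol 6.2.1 directs attention to drugs started after that study. Long-stopped drugs may therefore be few. All of this stands and limits the size of the point.

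Calling such drugs concomitant as a cautious convention does not stand. Caution is reasonable when timing is uncertain, but here the latest possible stop precedes first dose. Nor is it cautious to move a subject between the two AE groups.

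It can also be said that the end-date rule may mean a reported start only. Then the record keeps a stop of 31 March and an imputed start of 15 June, and meets both the prior and the concomitant definitions. The gap remains under either reading.

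A reader might infer more than the documents support:

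- **That any drug known to have stopped before Day 1 is affected.** A complete stop date prevents the error, and so does a start that is complete or known to the month.
- **That the rule for stopped drugs with no stop date has the same fault.** It reads "If a full date is missing and the status of the medication is not ongoing, impute date as the last dose date". Such a drug is not known to have ended before Day 1, and allowing for on-study use is a common convention.
- **That false protocol deviations follow**, because Protocol Appendix 1 prohibits antipsychotics in the first month. SAP 5.8 takes deviations from the deviation logs, not from imputed dates.
- **That a stated share of the antipsychotic-use group is false.** The documents give neither the frequency of these date patterns nor the rate of on-study antipsychotic use.

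**Conclusion.** The point holds in its narrow form. If the start is fully missing, or year-only in the first-dose year, and the stop is a month/year or year wholly before first dose, SAP 5.4.3 replaces recorded information with an imputed date and gives a class at odds with the intent of SAP 5.9.2. It is a missing check between two sets of rules, not a fault in the definitions.

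With a missing start, every record of this kind is misclassified. With a year-only start, only those in the first-dose year with a month/year stop are. The error runs one way, towards concomitant use. It reaches the concomitant and antipsychotic summaries, the count at first dose and the AE tables split by antipsychotic use. Because the record ends on Day 1, it does not reach the count at last dose unless the last dose was also on Day 1. The number of records cannot be derived from the documents, so the effect on any table is unknown.

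The result assumes that start dates are imputed first and that the end-date rule uses the imputed start. The illustrative dosing dates do not drive it.

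**What to change.** Add to SAP 5.4.3, to be applied before the rule that moves the end date to the start date:

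*If a partial medication stop date has its latest possible date before the first dose date, the medication is a prior medication; the stop date is imputed as that latest date, and any imputed start date later than it is set equal to it.*

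Keep the existing rule for all other cases. Deleting it, or extending the start guard to every imputed end date, would create a new error. Take a last dose on 15 November 2011 and a drug started in December 2011, not ongoing, with no stop date. The present rules give a start of 1 December and a stop of 15 November, which is reset to 1 December: post-treatment, as it should be. A guard applied to all imputed ends would pull the start back to 15 November and make the drug concomitant. SAP 5.9.2 summarizes post-treatment antipsychotics separately, so that would matter. The check proposed here does not touch this case, because it acts only on a partial stop before first dose.

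The cost is one sentence and a small program change. A count of the affected records, with antipsychotics shown separately, would supply the size that the documents do not give.

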## **5.5 Subject Enrollment and Disposition**

Subject enrollment by protocol amendments and subject counts by study center and prior study will be summarized.

A summary of subject disposition will display the number of subjects enrolled, received study drug, and remained in the study (using visit dates recorded on the vital signs CRF) at the beginning of the following time periods: first 4 weeks (Study Days 1 to 28), 1 to 3 months (Study Days 29 to 91), >3 to 6 months (Study Days 92 to 183), >6 month to 1 year (Study Days 184 to 365), >1 to 2 years (Study Days 366 to 730), >2 to 3 years (Study Days 731 to 1095), >3 to 4 years (Study Days 1096 to 1461) and >4 years (Study Days >=1462). Also included in this summary will be subject discontinuations showing the number of subjects who terminated from the study according to the reason for study termination/discontinuation (Investigator reported and Sponsor re-classified). Reasons for study termination will also be summarized by the time period specified above.

The withdrawal reasons as reported by the investigators on the eCRF are:

- Adverse event
- Death
- Disease progression
- Subject's voluntary withdrawal of consent (Voluntary withdrawal of consent)
- The Investigator determines that continuation in the study would be detrimental to a subject's well-being because of development of a serious illness, any other significant change in clinical status, or any other compelling medical reason (Investigator decision)
- Subject fails to comply with protocol requirements (Subject non-compliance)
- Lost to follow-up
- At discretion of Sponsor (Sponsor decision)

To better understand the discontinuation pattern, ACADIA reviewed the withdrawal reasons and in some cases, on the basis of verbatim comments in the eCRF, re-classified the reasons for discontinuation using the following categories:

- Adverse event
- Death
- Lack of efficacy / PDP progression
- PD /Concomitant disease progression
- Voluntary withdrawal of consent
- PDP improvement
- Investigator decision
- Subject non-compliance
- Lost to follow-up
- Sponsor decision

Subject disposition and study completion by Investigator-specified and Sponsor-reclassified reasons for termination will be presented in data listings and summary tables. Dispositions will also be summarized by 3 regions: North America (US and Canada), Europe and India.

## 5.6 Core Study Information

The core (preceding) study information (studies ACP-103-012, ACP-103-014, and ACP-103-020) will be summarized by protocol and will also be presented in a data listing.

## 5.7 Study Drug Exposure and Overall Compliance

### 5.7.1 Study Drug Exposure

For the final CSR, all subjects' study drug (pimavanserin) exposure will be calculated as last dose date minus first dose date + 1. For the interim report(s), the drug exposure will be censored at the database snapshot date for the on-going subjects. For example, if a subject had withdrawn from the study before the database snapshot, then the exposure duration for this subject is last dose date minus first dose date + 1; if a subject was still ongoing at the database snapshot date, then the exposure duration for this subject is database snapshot date minus first dose date + 1.

A summary of study drug exposure will include the duration of exposure as a continuous measure in days and a categorical measure for the intervals (1-28 days, 29-91 days, 92-183 days, 184-365 days, 366-730 days, 731-1095 days, 1096-1461 days,  $\geq 1462$  days). Total amount of administered pimavanserin (mg) will be estimated by (duration of exposure\*40 mg). Study drug exposure by Sponsor re-classified termination reasons will also be summarized. Study drug exposure for subjects who died will also be summarized.

Study drug exposure measures as described above will be presented in a listing.

Since this is an open-ending study, time on pimavanserin treatment (time on study) will be evaluated for all subjects and by subgroups: baseline age group ( $\leq 75$  years old or  $> 75$  years old), gender (female or male), and geographic area (North America or outside North America). For subjects who have discontinued from study, the days on pimavanserin treatment in study -015 (not counting the exposure duration from the preceding study) will be calculated as last dose date minus first dose date + 1; otherwise the time on study will be censored at database snapshot date and will be calculated as database snapshot date minus first dose date + 1. Kaplan-Meier estimates of percent subjects on treatment at 6 months (183 days), 1 year (365 days), 1.5 years (548 days), 2 years (730 days), 2.5 years (913 days), 3 years (1095 days), 3.5 years (1278 days) and 4 years (1461 days), as well as median days on treatment will be presented.

In addition, Kaplan-Meier estimates percent subjects free of AEs leading to study termination or drug withdrawal and median days to due to AEs leading to study termination or drug withdrawal will be summarized for all subjects and by

aforementioned subgroups. For this analysis, if a subject has an AE leading to study termination or drug withdrawal, the time to event will be calculated as last dose date minus first dose date + 1; otherwise the time to event will be censored at either last dose date (for subjects who discontinued due to reasons other than AE) or database snapshot date (for ongoing subjects).

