3.3 Study Duration

The duration of treatment for any individual subject will be determined based on clinical grounds, but may continue for as long as pimavanserin is considered to be tolerated and beneficial, or until such time as pimavanserin is approved and commercially available.

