13.5 Protocol Amendments and Study Termination

Protocol amendments must be made only with the prior approval of ACADIA and documented approval/favorable opinion of the IRB or EC of an amendment, except where necessary to protect the safety, rights, or welfare of subjects. Agreement from the Investigator must be obtained for all protocol amendments and amendments to the Informed Consent document. The IRB or EC must be informed of all amendments and give approval for any amendments likely to affect the safety of the subjects or the conduct of the trial. The Investigator must send a copy of the approval letter from the IRB or EC to ACADIA and/or designee.

Both ACADIA and the Investigator reserve the right to terminate the study, according to the study contract. The Investigator should notify the IRB or EC in writing of the trial's completion or early termination and send a copy of the notification to ACADIA and/or designee.

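### The Kaplan-Meier rule for time on treatment (SAP 5.7.1) fits an interim snapshot but does not correctly handle subjects still on pimavanserin when the study closes

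*SAP*

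**What the plan says.** **The rule (SAP 5.7.1).** Time on treatment has two branches.
- "For subjects who have discontinued from study, the days on pimavanserin treatment in study -015" run from first to last dose, with no split by reason for stopping.
- For everyone else, "otherwise the time on study will be censored at database snapshot date".

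The outputs are percent on treatment at 183, 365, 548, 730, 913, 1095, 1278 and 1461 days, "as well as median days on treatment will be presented", overall and by age group, sex and geographic area.

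**The final report (SAP 5.7.1, opening sentence).** "For the final CSR, all subjects' study drug (pimavanserin) exposure will be calculated as last dose date minus first dose date + 1". The exposure summary therefore has separate final and interim rules. The Kaplan-Meier paragraph has only one.

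**How treatment can end.** Protocol 3.3 lets a subject continue while the drug is tolerated and beneficial, "or until such time as pimavanserin is approved and commercially available". Protocol 13.5 adds: "Both ACADIA and the Investigator reserve the right to terminate the study".

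**Reasons for leaving (SAP 5.5).** Neither the investigator list nor the sponsor-reclassified list has an entry for study closure or a move to commercial drug. The nearest is sponsor decision.

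**Parallel analyses.** For AE-related stopping, SAP 5.7.1 has time "censored at either last dose date (for subjects who discontinued due to reasons other than AE", or at the snapshot for ongoing subjects. The survival analysis in SAP 5.13.2 likewise censors living discontinued subjects at last dose and ongoing subjects at the snapshot.

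**The concern.** A subject still taking pimavanserin when the study closes has not stopped for any reason connected with the drug. The calendar ended the observation, so the time should be censored at last dose. The stated rule offers only an uncensored stop at last dose or censoring at a snapshot date, and neither is right for this subject.

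At stake are the later landmarks and possibly the median in the final report. If closures count as stops, those figures partly measure how long before closure each subject was enrolled. The study has no comparator and no formal tests, so readers will take the percentages at face value. The exposure summary by reclassified reason would also mix closures with sponsor-ordered withdrawals.

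**Working it through.** The documents give no Kaplan-Meier figure to reproduce, and SAP 2.4 lists sample size as not applicable. The check is therefore the logic of the rule, followed by illustrations on assumed inputs.

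**1. Where a closure subject falls at the final report**

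| Reading | Treatment of the subject | Effect on the curve |
|---|---|---|
| Discontinued from study | Event at last dose | Too low |
| Completer, hence the remaining branch | Censored at a snapshot after last dose | Too high: credits time off drug |
| Neither reading offers | Censored at last dose | Correct |

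**2. Ten-subject example.** Five true stops at days 100, 200, 300, 400 and 600; five subjects on drug at closure at days 700, 800, 900, 1000 and 1200.
- Closures censored at last dose: 70% on treatment at 365 days, 50% at 730, 50% at 1095.
- Closures as events: 70%, 40%, 10%, and 0% from day 1200. With no censoring, the curve must end at zero.

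**3. Closed form for closures counted as events.** Assume uniform entry over 5 years, a constant stopping rate, and closure c years after the last entry. Then:

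reported S(t) = 2^(−t/m) × P(t), where m is the true median in years, P(t) = 1 for t ≤ c, and P(t) = (c + 5 − t)/5 for t > c.

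For m = 2 and c = 1:
- 2 years: 0.500 × 4/5 = 40.0%, against a true 50.0%.
- 3 years: 0.354 × 3/5 = 21.2%, against 35.4%.
- 4 years: 0.250 × 2/5 = 10.0%, against 25.0%.
- Median: 1.62 years, against 2.0.
- On drug at closure: (1/5) × (2/ln 2) × (2^(−0.5) − 2^(−3)) = 33.6%.

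Across m = 1 to 3 and c = 1 to 3, the 4-year shortfall runs from 1.25 points (m = 1, c = 3: 6.25% × 1/5) to 23.8 points (m = 3, c = 1: 39.7% × 3/5). For c ≥ 4, P(4) = 1 and there is no shortfall at any planned landmark.

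**4. Simulation with a different follow-up assumption.** N = 400 (the anticipated minimum in Protocol 3.4), exponential stopping, uniform time from first dose to closure, 60 replicates per scenario. Each cell gives closures censored at last dose / closures as events.

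| True median (days) | First dose to closure (days) | On drug at closure | 2 years (%) | 3 years (%) | 4 years (%) | Median (days) |
|---|---|---|---|---|---|---|
| 365 | 365–1825 | 17% | 25.2 / 18.9 | 12.2 / 6.1 | 5.8 / 1.5 | 364 / 362 |
| 730 | 365–1825 | 38% | 49.4 / 36.9 | 34.9 / 17.2 | 24.7 / 6.2 | 719 / 564 |
| 730 | 730–2190 | 27% | 49.9 / 49.9 | 35.1 / 26.2 | 24.7 / 12.3 | 729 / 720 |
| 1095 | 365–1825 | 52% | 62.8 / 47.3 | 50.3 / 25.3 | 39.5 / 9.9 | 1111 / 695 |

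The largest 4-year gap is 39.5 − 9.9 = 29.6 points. When every subject was first dosed more than 1461 days before closure, the two curves agree at every landmark. The 1-year figures agree in all scenarios because no closure was assumed before day 365.

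**5. The completer reading.** With an assumed 90 days from last dose to snapshot, estimates rise by 0 to about 3 points. The largest rise is at 4 years with a true median of 1095 days and closure at 365–1825 days: 42.4% against 39.5%.

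**6. What the documents say about follow-up.** Protocol 1.2 gives 160 active subjects on 1 May 2010 and 77 who had received drug for more than 12 months, so at least 160 − 77 = 83 active subjects had 12 months or less. From 1 May 2010 to the snapshot of 13 December 2013 is 1322 days. For anyone dosed by May 2010, closure after the snapshot leaves all landmarks through 1278 days untouched. The 1461-day landmark is also safe if closure came at least 1461 − 1322 = 139 days after the snapshot. Protocol 1.3 says further blinded studies were being planned, so later entry was foreseeable, but neither numbers nor dates are given.

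**The case against.** The strongest reply is that no section says closure is an event. Protocol 10.2.2 separates completers from early withdrawals, and SAP 5.5 refers to study completion, so a subject on drug at closure could be a completer and be censored. That stands as far as it goes: counting closure as stopping is an inference. It does not rescue the rule. The SAP never defines a completer, the parallel analyses recognise only discontinued and ongoing subjects, and the completer reading still censors after last dose.

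Second, the size may be nil. The documents give no closure date, approval date or number on drug at closure, and the dates above protect most landmarks for early entrants. This stands in full. Bias at a landmark arises only through subjects closed out before reaching it.

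Third, the curve is a descriptive item in an exposure section. Protocol 6.1 measures the primary objective by AEs, laboratory tests, ECG, vital signs and physical examinations. The AE-stopping and survival curves already censor other exits at last dose. Disposition by reason and time period would also let a reader see a late block of sponsor-decision exits, though that category is not specific to closure. All of this limits the severity.

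A reader might also infer that the North America comparison is distorted by approval timing. That needs closure dates that differ by region, which the documents do not mention.

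**Conclusion.** The concern holds for the final report. At that point no subject is ongoing, and both available readings mishandle a subject on drug at closure: one biases the curve down, the other biases it up by less.

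The size cannot be fixed from the documents. With assumed true medians of 1 to 3 years and the closure patterns above, the downward bias at 4 years runs from 0 to roughly 24 points (closed form) or 30 points (simulation). The simulated median falls by 0 to 1111 − 695 = 416 days. Entry pattern, stopping rate, closure timing and the 90-day lag are all assumptions.

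The documents do not support three stronger conclusions: that the plan expressly counts closure as stopping drug, that the interim analysis for the NDA is wrong, or that the main tolerability results are affected. No error rate is involved, because SAP 5.1 plans no formal tests. The severity is moderate.

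**What to change.** In SAP 5.7.1, state for the time-on-treatment analysis: *In the final report, subjects whose treatment ends because the study or site is closed, or because they move to commercial pimavanserin, are censored at last dose date. All other discontinuations are events at last dose date. At an interim, ongoing subjects are censored at the snapshot date.*

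In SAP 5.5, add a sponsor-reclassified reason, *study closed / transition to commercial drug*, so that these subjects can be identified and kept apart from sponsor-ordered withdrawals.

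The cost is one short rule and one category. Last dose date is already collected on the discharge eCRF (SAP 5.4.3), and reclassification from verbatim comments is already planned (SAP 5.5). The interim needs no rerun. Make the change before final database lock.
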